Cover Page for ClinicalTrials.gov

Document:

Study Protocol and Statistical Analysis Plan

Official Title of the Study

Effect Of Hot Saline Irrigation on the Operative Field During Endoscopic Sinus Surgery: A Randomized Controlled trial

Date of the Document: 16th May, 2023

[name], Department of ENT, Benazir Bhutto Hospital, Rawalpindi Medical University and Allied Hospitals, Rawalpindi

Introduction

Chronic rhinosinsusitis is an inflammatory disease of the sinonasal mucosa lasting for more than 12 weeks. Endoscopic sinus surgery is the surgical procedure used to treat recalcitrant chronic rhinosinusitis. It not only helps in the drainage of sinuses and removal of pathology but also prevents the disturbance of anatomy and formation of facial scars. Control of bleeding during the procedure is a test for surgeons as well as anesthetists.

Hot normal saline with a temperature of 50°C causes dilatation of vessels and nasal edema without causing mucosal necrosis, it not only helps in control of bleeding via compression of vasculature but also promotes the clotting pathways.⁵

A study conducted by Shehata A et al. showed a significant improvement in the operative field when hot normal saline at 50° C was used during endoscopic sinus surgery with a mean and standard deviation of 1.96±0.67 as compared to the control group (2.64±0.7).⁵ A study by Ranford D et al. concluded that irrigation with heated saline during endoscopic sinus surgery reduced bleeding by 20 percent.⁷ Moreover it also decreased the duration of patient's surgery by 9 minutes. ⁶

The aim of this study is to evaluate the effect of hot saline irrigation during endoscopic sinus surgery. The additional advantages provided by irrigation of hot saline will not only provide superior post-operative results but will also reduce the duration of surgery.

Objective

To determine the effect of hot saline irrigation on the operative field during endoscopic sinus surgery.

Hypothesis

Hot saline irrigation provides good control of bleeding during endoscopic sinus surgery.

Operational Definitions

Endoscopic Sinus Surgery: An endonasal surgery done via endoscope using instruments for drainage of sinuses and removal of sinonasal pathology.

Hot Normal Saline: A solution formed by dissolving 0.9 grams of NaCl in 100ml of water and warmed up to 50°C.

Mean Arterial Pressure: It is an average pressure present in the arteries in one cardiac cycle calculated by addition of diastolic blood pressure with 1/3rd of the pulse pressure.

Boezaart Score: 5

Grades Assessment

- 0- No bleeding (cadaveric conditions)
- 1- Slight bleeding: no suctioning required.
- 2- Slight bleeding: occasional suctioning required.
- 3- Slight bleeding: frequent suctioning. Bleeding threatens surgical feld a few seconds after suction is removed.
- 4- Moderate bleeding: frequent suctioning required and bleeding threatens surgical field directly after suction is removed.
- 5- Severe bleeding: constant suctioning required; bleeding appears faster than can be removed by suction; surgical field severely threatened and surgery usually not possible.

Methods & Materials

Study Design: Randomized controlled trial

Study Setting: Department of ENT, Benazir Bhutto Hospital

Study Duration: After the approval of the topic till completion of sample size

Sample Size:

By using WHO sample size calculator

Sample size n = 60 (30 in each group)

Level of significance = 5%

Power of test = 90%

Test value population mean = 1.96⁵

Anticipated population mean = 2.64⁵

Population standard deviation = 0.685⁵

Sampling Technique: Simple random sampling

Sample Selection

Inclusion Criteria

Patients bilateral chronic rhinosinusitis refractory to medical treatment and requiring surgical intervention.

Exclusion Criteria

- 1. Patients with malignancies.
- 2. Patients with unilateral disease
- 3. Bleeding diathesis
- 4. Uncontrolled hypertension
- 5. Long term usage of NSAIDS and anti-coagulants.

Data Collection Procedure

This research will be carried out after approval from the Ethical Review Board of Rawalpindi Medical University. Patients requiring surgical intervention for chronic rhinosinusitis will be selected via simple random sampling. They will be divided into 2 groups via randomization (30 patients in each group) and undergo endoscopic sinus surgery in the operation theatre of Benazir Bhutto Hospital. Double blinding will be done. Surgery will be performed by a consultant with an experience of more than 5 years. For the intervention, normal saline will be warmed in a boiler up to 50°C and temperature will be continuously checked with the help of a thermometer. Group A will have irrigation of nasal cavities with hot normal saline (of 50°C) during the operation. Group B will have irrigation with saline at room temperature. This is a double blinded RCT in which the patient and the operating surgeon will not know about the specific intervention. Bleeding score will be checked via Boezaart score. More over, duration of the procedure and mean arterial pressure of all patients will also be documented. The researcher will collect the data by herself to avoid bais.

Data Analysis

Data will be analysed with help of SPSS version 26. Qualitative variables will be represented as frequencies and percentages. Quantitative variables will be represented via mean and standard deviation. Chi square test will be applied. Furthermore, logistic regression will be done. Data will be documented in tabular form. A P-value of <0.05 will be considered significant.

References

- 3. Alkan A, Honca M, Alkan A, Güleç H, Horasanlı E. The efficacy of esmolol, remifentanil and nitroglycerin in controlled hypotension for functional endoscopic sinus surgery. Braz

- J Otorhinolaryngol. 2021 May-Jun;87(3):255-259. Doi: 10.1016/j.bjorl.2019.08.008. Epub 2019 Oct 3. PMID: 31668787; PMCID: PMC9422684.

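### No mucosal injury or adverse event is planned to be recorded in either arm, so the trial could report a benefit of 50°C saline with no such harm counts beside it

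*Combined protocol and SAP*

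**What the plan says.** The Data Collection Procedure sets the allocation, "They will be divided into 2 groups via randomization (30 patients in each group", and the two exposures: "Group A will have irrigation of nasal cavities with hot normal saline", at 50°C and while surgery is under way, and "Group B will have irrigation with saline at room temperature". Three variables are named for recording. The first is the bleeding grade ("Bleeding score will be checked via Boezaart score"). The other two come in one sentence: "duration of the procedure and mean arterial pressure of all patients will also be documented".

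The Introduction describes saline at 50°C as a treatment that "causes dilatation of vessels and nasal edema without causing mucosal necrosis", with reference 5 cited for the sentence.

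The same section plans an exposure check, "temperature will be continuously checked with the help of a thermometer", and ethics board approval before the study starts. The Objective concerns the operative field and the Hypothesis concerns control of bleeding. The Data Analysis section lists descriptive summaries, a chi-square test and logistic regression. No section mentions adverse events, complications, examination of the mucosa, post-operative follow-up or a safety summary. The text at these places is continuous, with no redaction.

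**The concern.** The protocol names one specific harm that heat might cause, cites a source for its absence, and then plans no variable that could show it. If the plan is followed exactly, a mucosal injury in either arm goes uncounted. The report could then give a difference in bleeding grade by arm and, on injury, could only repeat the cited statement. Data that were not collected cannot be recovered at analysis.

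Two things are at stake. The first is patient safety, because 30 people receive the heated irrigation. The second is what the result can be used for. A reader deciding whether to adopt heated irrigation needs harms as well as benefit from the same randomised comparison. The room-temperature arm is the right comparator here: both arms have endoscopic surgery, so ordinary surgical trauma occurs in both, and a difference in injury counts would be informative in a way that a single-arm count is not.

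**Working it through.** **1. Planned variables against kinds of harm**

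| Kind of harm | Planned variable that would show it |
|---|---|
| Worse bleeding | Boezaart grade (0 to 5) |
| Longer surgery | Duration of the procedure |
| Change in blood pressure | Mean arterial pressure |
| Mucosal injury or necrosis | None |
| Any other intra-operative or in-hospital event | None |

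The thermometer reading describes the saline, not the tissue, so it is not an outcome.

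**2. The plan's own figures.** The documents give no injury rate and no safety calculation, so there is no safety figure to reproduce. The only input needed is the arm size, n = 30, which the Sample Size and Data Collection Procedure sections state consistently. The stated efficacy inputs (difference 2.64 − 1.96 = 0.68, SD 0.685, 5% significance, 90% power) do not themselves lead to 30. The two-sided normal formula gives 2 × [0.685 × (1.960 + 1.282) / 0.68]² ≈ 21.3, or 22 per group. This does not affect the present point, which uses the 30 actually planned.

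**3. What zero events in 30 would show.** If the true rate is q, the chance of no event is (1 − q)^30. Solving for the largest compatible q:

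- one-sided 95%: 1 − 0.05^(1/30) = 1 − 0.9050 = 9.5%
- two-sided 95% (Clopper-Pearson): 1 − 0.025^(1/30) = 1 − 0.8843 = 11.6%

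**4. Chance of seeing at least one event in 30.** The formula is 1 − (1 − q)^30. The rates are assumptions chosen to show the range.

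| Assumed true rate q | (1 − q)^30 | Chance of at least one case |
|---|---|---|
| 1% | 0.740 | 26% |
| 2% | 0.545 | 45% |
| 5% | 0.215 | 79% |
| 10% | 0.042 | 96% |

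These are upper limits, because they assume that every injury is seen and recorded.

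**5. Whether a test between arms would help.** With 0/30 in controls, Fisher's exact test gives p = 0.052 for 5/30 in the hot-saline arm and p = 0.024 for 6/30, so at least 6 cases are needed for p < 0.05. Against an assumed control rate of 1%, its power is about 6% at a hot-saline rate of 10%, 48% at 20% and 86% at 30%. A test would miss most plausible differences, so counts with intervals are the right summary.

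**The case against.** The strongest reply is that the trial was not designed to study safety. The statement about necrosis is one cited clause of background. The case for the trial in the Introduction rests on a better operative field, 20 percent less bleeding and 9 minutes saved. Safeguards exist: the temperature is checked throughout and an ethics board must approve the study. With 30 per arm, recording injury could not settle the matter anyway. An end-of-surgery judgement of thermal injury would also be hard to make in mucosa that has just been operated on.

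Much of this stands. The trial is not obliged to test the clause, and whether reference 5 supports it cannot be checked from the documents. The safeguards are real, although neither yields counts by arm. The difficulty of attributing injury to heat is a reason to define the item and leave cause out of it, so that the comparison between arms does that work. The small sample limits what may be claimed, but it does not justify collecting nothing.

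A reader might infer that the trial records no harm of any kind. The documents do not support that: the Boezaart scale extends to bleeding too severe for surgery to continue in most cases, and mean arterial pressure is taken in all patients. A reader might also count oedema as an unrecorded harm, but the Introduction presents it as part of how the treatment works. Finally, the documents include no data collection form, so the gap is in the variables the protocol names. What a form might contain is unknown.

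**Conclusion.** The concern holds in a limited form. Bleeding and blood pressure are captured. Mucosal injury and adverse events are not, for an exposure that the protocol itself describes by reference to necrosis. The comparison of bleeding grades is unaffected. What is lost is the harm side of the randomised comparison.

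If the items were recorded, zero cases in 30 would leave rates up to 9.5% (one-sided) or 11.6% (two-sided) open. The chance of at least one case would run from at most 26% at an assumed rate of 1% to at most 96% at 10%. As planned, the trial gives no bound at all.

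These figures assume that all 30 patients are assessed, that patients are independent, and that detection is perfect. The documents supply none of the rates.

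It is tempting to conclude that recording injury would let the trial confirm its background statement. It would not. It could reveal or bound common injury, but it could neither establish the absence of necrosis nor exclude delayed injury after discharge.

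**What to change.** In the Data Collection Procedure, add two items for both groups:

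1. **Mucosal injury at the end-of-surgery endoscopic view.** Give a written definition, fixed before the first patient. The operating surgeon, whom the protocol describes as blinded, records yes or no without attributing cause. Since all patients have bilateral disease, count each patient once.
2. **Any intra-operative or in-hospital adverse event up to discharge**, taken from the routine record.

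In Data Analysis, add one table of counts by arm with exact 95% confidence intervals, labelled descriptive and without hypothesis tests. State that zero events would not demonstrate safety and that injury appearing after discharge is not covered.

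The cost is a little extra recording per case. The first item uses a view that the surgery already provides. The second asks the researcher to look at the in-hospital record, a step the protocol does not currently describe. Neither item changes the treatment, the sample size or the primary comparison.

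### The trial is sized on a difference in mean Boezaart scores, but the only analyses named are chi-square and logistic regression; compare one value per patient as means instead

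*Combined protocol and SAP*

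**What the plan says.** The Objective is stated as "To determine the effect of hot saline irrigation on the operative field during endoscopic sinus surgery". The Operational Definitions give the Boezaart score as six ordered grades, 0 to 5; grade 2, for example, reads "Slight bleeding: occasional suctioning required".

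The Sample Size section sets 30 patients per group at 5% significance and "Power of test = 90"%. Its inputs are means of 1.96 and 2.64 and an SD of 0.685. The Introduction shows that these are operative-field values from a cited study (1.96 with SD 0.67 for hot saline, 2.64 with SD 0.70 for control).

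The Data Collection Procedure says of the outcome only "Bleeding score will be checked via Boezaart score". It does not say when the grade is taken, how often, or how two operated sides become one value, although the Inclusion Criteria require bilateral disease.

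Data Analysis describes quantitative variables by mean and SD. For the comparison between groups it says only "Chi square test will be applied. Furthermore, logistic regression will be done". Neither method is linked to a variable.

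**The concern.** A sample size holds only for the analysis it was computed for. Here it was computed for a difference in means, and no comparison of means is planned.

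If chi-square is meant for the Boezaart score, it treats six ordered grades as unordered categories and discards the information that a treatment shifting grades downwards would produce. If the score is to be made binary for chi-square or logistic regression, the cut-off is missing and could be chosen after the data are seen. If neither method is meant for the score, the outcome on which the trial is sized has no named test. On every reading, the stated 90% power is not tied to an analysis in the plan.

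**Working it through.** **Inputs.** From Sample Size: means 1.96 and 2.64 (difference 0.68), SD 0.685, alpha 5%, power 90%, 30 per group. Two-sided testing is assumed, since the plan does not say. From the Operational Definitions: grades 0 to 5.

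**1. The plan's own figure.**
n per group = 2 × (SD/difference)² × (1.960 + 1.282)² = 2 × (0.685/0.68)² × 10.51 = 21.3, so 22 per group. A t-based calculation gives 23 (90.9% power). The stated 30 is not reproduced; it is larger than the inputs require, and no dropout allowance is stated to explain the gap.

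**2. Comparison of means at 30 per group.**
Non-centrality = (0.68/0.685) × √(30/2) = 3.845. Normal approximation: Φ(3.845 − 1.960) = Φ(1.885) = 97.0%. The exact t calculation gives 96.6%.

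**3. Chi-square on the same inputs.** The plan gives no grade distribution, so one is assumed: normal values rounded to grades 0-5, fitted so that the graded means are 1.96 and 2.64 and the graded SD is 0.685 in both arms. The resulting proportions are:

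| Grade | 0 | 1 | 2 | 3 | 4 | 5 |
|---|---|---|---|---|---|---|
| Hot saline | 0.009 | 0.220 | 0.578 | 0.186 | 0.007 | 0.000 |
| Control | 0.000 | 0.033 | 0.378 | 0.506 | 0.082 | 0.001 |

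Simulated power at 30 per group (40,000 trials):

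| Analysis | Power |
|---|---|
| t test on grades | 97% |
| Mann-Whitney | 96% |
| Chi-square, all grades | 86% |
| Chi-square, three levels (≤1, 2, ≥3) | 91% |
| Chi-square, ≤2 versus >2 | 90% |
| Chi-square, ≤1 versus >1 | 69% |
| Chi-square, ≤3 versus >3 | 20% |

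Hand check of the ≤2 cut: proportions 0.807 and 0.411, difference 0.396, pooled 0.609. Null SE = √(2 × 0.609 × 0.391/30) = 0.126; alternative SE = √((0.807 × 0.193 + 0.411 × 0.589)/30) = 0.115. Power = Φ((0.396 − 1.96 × 0.126)/0.115), about 90%.

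**4. Sensitivity to the assumed SDs.**
- With the arm-specific SDs (0.67 and 0.70) matched after rounding: t test 96.7%, Mann-Whitney 96.3%, full-table chi-square 85.6%, ≤2 cut 91.1%, ≤3 cut 23.9%.
- With those SDs applied before rounding, so that the graded SDs are larger (0.73 and 0.76): t test 93.7%, Mann-Whitney 93.0%, full-table chi-square 77.0%, ≤2 cut 85.1%, ≤3 cut 33.0%.

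The full-table chi-square therefore loses about 11 to 17 percentage points against a comparison of means.

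**5. Sparse cells.** In about 99% of the simulated full tables, more than 20% of cells had an expected count below 5, so the chi-square approximation is itself doubtful in the uncollapsed form.

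**The case against.** The plan never says that chi-square is for the Boezaart score, still less on an uncollapsed six-grade table. Sparse tables are commonly collapsed, and two natural groupings reach 90% or a little more. A linear-by-linear chi-square, which uses the order of the grades, has 96.5% in the same simulation. So does a logistic regression of arm on grade. This stands to the extent that chi-square cannot be called underpowered in every form. It does not rescue the plan, because none of these forms is stated and the unfavourable cut-offs are just as open.

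The sample exceeds what its inputs need, so some loss could be absorbed. That is true for a comparison of means. Under full-table chi-square the margin is used up: 90% is reached only at about 34 per group, on the assumed shape.

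A reader might also infer that the silence on readings produces a diluted effect or a false-positive rate above 5%. If 20% of Group A grades resembled control, the difference would be 0.8 × 0.68 = 0.544 and power for means would fall to 83%. If two sides were analysed as independent, true alpha would be 2 × (1 − Φ(1.96/√(1 + ρ))), or 8.6% to 13.3% for ρ from 0.3 to 0.7. The documents support neither inference. They count patients, 30 in each group, not sides, and the objective concerns the field during surgery, for which one overall grade per operation is the natural reading. The 20% and the correlations are assumptions. These figures are conditional illustrations only.

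Finally, a rank test does almost as well as a t test. Comparing means is preferred because it matches the sample-size basis, not because it is the only valid choice.

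**Conclusion.** The concern holds as a mismatch between the sample size and the analysis. The trial is sized for a difference in means, and no test of means or ranks is named for the score. At 30 per group a comparison of means has about 97% power on the plan's inputs. Chi-square across all grades has about 86%, and a two-level split has about 20% to 91% depending on an undefined cut-off.

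The 97% rests on the plan's difference and SD. The chi-square figures rest also on a rounded-normal grade distribution, and 77% is possible for the full table under a wider SD. The documents do not say whether the source means and SD describe single or averaged grades, so no gain from averaging can be claimed, and the 97% assumes that the value analysed behaves like the source values.

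One might conclude that the trial is too small. It is not: 30 per group exceeds the 22 or 23 that the inputs require, provided the analysis is the one assumed. The absent reading points are missing detail, not evidence that grades will be taken badly.

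**What to change.** In Data Analysis, state that:

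- the primary outcome is one Boezaart value per patient, obtained in the same way in both arms after irrigation has begun;
- groups are compared on it by the difference in means with a 95% confidence interval (t test or linear regression), with Mann-Whitney as a sensitivity analysis;
- this replaces chi-square for this outcome, and chi-square is kept for qualitative variables;
- if logistic regression is retained, its outcome, any cut-off and its covariates are given in advance.

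In the Data Collection Procedure, state who assigns the grade. That section says that "the patient and the operating surgeon will not know about the specific intervention" and also that the researcher collects the data herself. It should be clear which of them grades the field and whether that person is blinded.

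Several readings per side, or a grade before the first irrigation as a covariate, are optional. Any benefit depends on correlations the documents do not give. If several readings are used, tying them to steps of the operation would keep them comparable between arms, since the Introduction expects that hot saline "will also reduce the duration of surgery".

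The cost is a few sentences and a different procedure in the same software. No extra patients are needed.

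### Does leaving the timing and analytic role of mean arterial pressure unstated put the bleeding comparison at risk?

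*Combined protocol and SAP*

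**What the plan says.** MAP appears twice. Operational Definitions gives a formula, diastolic pressure plus a third of the pulse pressure, and describes it thus: "It is an average pressure present in the arteries in one cardiac cycle". The Data Collection Procedure adds: "More over, duration of the procedure and mean arterial pressure of all patients will also be documented". Neither place gives a time, a number of readings, or a rule for reducing several readings to one value.

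The outcome is introduced just before: "Bleeding score will be checked via Boezaart score". Data Analysis does not mention MAP by name. Three of its sentences bear on the point:

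- "Quantitative variables will be represented via mean and standard deviation", which covers MAP as a descriptive variable.
- "Chi square test will be applied", with no variables named.
- "Furthermore, logistic regression will be done", with no dependent variable and no covariates named.

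Blood pressure also appears in the Exclusion Criteria, as "Uncontrolled hypertension", with no threshold.

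**The concern.** MAP is one of only two extra variables the protocol undertakes to record, it has its own operational definition, and a regression is promised. It is therefore an obvious candidate covariate, yet the plan neither includes it nor excludes it.

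Three things could be at stake:

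- **False positives.** If the choice is made after the data are seen, the better-looking of two results can be reported, and the error rate exceeds 5%.
- **Interpretation.** A reading taken before irrigation can serve as a baseline covariate. A reading taken once irrigation has begun comes after treatment, and adjusting for it could remove part of the effect or introduce bias.
- **Precision.** If MAP predicts bleeding, leaving it out gives up some power or a narrower interval.

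**Working it through.** **Inputs.** From Sample Size: means 1.96 and 2.64 (difference 0.68), SD 0.685, 30 per group, 5% significance, 90% power. Assumed, because the documents give no value: the correlation r between MAP and the underlying bleeding score, taken from 0 to 0.5.

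**The plan's own figure.** With a two-sided test and the normal formula, n per group = 2 × (0.685 × (1.960 + 1.282) / 0.68)² = 21.3, so 22 per group. The plan has 30. Power at 30: 0.68 / (0.685 × √(2/30)) = 3.845; 3.845 − 1.960 = 1.885; Φ(1.885) = 97.0% (96.6% with the t distribution). The stated inputs do not reproduce 30, but the trial is larger than they require, so MAP adjustment is not needed to rescue power.

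The 97% applies to a mean comparison on a continuous score. The Boezaart score is a whole number from 0 to 5.

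**Simulation model.** Latent score = group mean + 0.685 × (r × MAP + √(1 − r²) × error), with MAP standardised and unaffected by treatment, rounded to a whole grade and limited to 0 to 5; 30 per group. Rounding raises the SD to 0.74. The unadjusted analysis is a t-test; the adjusted one is ANCOVA with MAP as covariate.

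| r | False-positive rate, one fixed model | False-positive rate, smaller p of the two | CI width, adjusted / unadjusted (median) | Power at 0.68, unadjusted | Power at 0.68, adjusted |
|---|---|---|---|---|---|
| 0 | 5.1% | 5.6% | 1.009 | 93.6% | 93.2% |
| 0.3 | 5.0% | 6.3% | 0.977 | 93.6% | 94.9% |
| 0.5 | 5.1% | 7.2% | 0.901 | 93.7% | 97.3% |

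The width ratio is 1.008 at r = 0.1 and 0.998 at r = 0.2, so adjustment breaks even just below 0.2. A fresh run of 100,000 trials per value of r agreed with the table to within about 0.2 percentage points on error rates and power and 0.001 on the width ratio.

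**Reading the results.**

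1. Either model, fixed in advance, holds 5% whatever r is. Chance imbalance in MAP is not a bias, and the unadjusted standard error already allows for it.
2. The excess in the third column is 0.5 to 2.1 percentage points (5.6 − 5.1 and 7.2 − 5.1). It arises only if the analyst fits both models and always reports the smaller p-value. The plan names neither a t-test nor ANCOVA.
3. Excluding uncontrolled hypertension probably narrows the spread of MAP, which tends to lower r. At r of 0 to 0.1, adjustment widens the interval by slightly under 1%.
4. On the same integer-grade model, a chi-square test across all grades has about 77% power, against about 94% for an unadjusted comparison of means. That gap of about 17 points comes from the choice of primary test. Adjusting for MAP changes power by −0.4 to +3.6 points (93.2 − 93.6 and 97.3 − 93.7).

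**The case for a change.** The strongest case for acting has three parts.

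First, a baseline reading that is never taken cannot be recovered at analysis, so this is a data-collection point as well as a wording point, and naming the primary test would not by itself fix the reading time. That is correct as far as it goes. But the loss matters for inference only if MAP is to be a covariate, and the documents give no ground for expecting a worthwhile gain.

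Second, the table understates the freedom available, because it allows only one reading. With two candidate readings (assumed correlation 0.7, both treated as unaffected by treatment), reporting the smallest p-value gives 5.8%, 6.7% and 7.9% at r = 0, 0.3 and 0.5. This stands as arithmetic. It still needs deliberate selection among models the plan does not mention, and the excess stays below 3 points.

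Third, adjusting for an intra-operative reading could mislead. This also stands, as a caution on interpretation. It would affect a secondary adjusted result and leave the randomised unadjusted comparison intact.

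Finally, a written decision not to adjust would close the gap as well as a decision to adjust. If either choice is acceptable, what is missing is a recorded detail; the plan does not contain a wrong method.

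**Conclusion.** The observation is accurate: the plan gives no reading time and no stated role for MAP. No change follows from it. The natural reading is that MAP is recorded alongside duration of the procedure and summarised by mean and SD, and nothing in the text proposes adjusting the bleeding comparison for it. On that reading the randomised comparison is valid at 5%. An analyst who did consider adjustment would be expected to know that only a pre-irrigation reading is suitable.

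At worst the gap adds about 0.5 to 2 percentage points to the false-positive rate for one reading, and less than 3 for two, conditional on selective reporting and on an assumed r of 0 to 0.5. Making MAP-adjusted ANCOVA the primary analysis is not shown to help. It slightly widens the interval when r is below about 0.2, no r is documented, and no pre-irrigation reading is shown to be collected. These figures rest on normal latent scores rounded to whole grades, with r being the correlation with the score before rounding.

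The unnamed primary analysis is a separate and larger matter, and whether MAP is a covariate is settled when that analysis is named.

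### Shorter surgery is an expected benefit, but the plan names no pre-operative measure of extent and no model for minutes, so its power for the cited 9-minute saving depends on an SD it does not give

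*Combined protocol and SAP*

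**What the plan says.** The Introduction cites earlier work on duration: "Moreover it also decreased the duration of patient's surgery by 9 minutes". Its closing paragraph, on the aim of the study, adds that hot saline "will also reduce the duration of surgery". The Objective is narrower: "To determine the effect of hot saline irrigation on the operative field during endoscopic sinus surgery". The Hypothesis likewise concerns control of bleeding only.

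The single inclusion criterion reads "Patients bilateral chronic rhinosinusitis refractory to medical treatment and requiring surgical intervention". The exclusions remove unilateral disease, malignancy, bleeding diathesis, uncontrolled hypertension and long-term NSAID or anticoagulant use. Nothing restricts polyps, previous sinus surgery, severity or the number of sinuses to be opened.

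Under Data Collection Procedure, bleeding is graded on the Boezaart scale and "duration of the procedure and mean arterial pressure of all patients will also be documented". No other measurement is named, and no stratification is described. Data Analysis names means and SDs, a chi-square test and logistic regression. It does not state an outcome or covariates for the regression.

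The sample size of 30 per group rests on Boezaart inputs alone. No SD, mean or power is given for duration.

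**The concern.** A limited first operation and an extensive revision with polyps both fit the inclusion criterion, provided the disease is bilateral. How much surgery a patient needs is settled before allocation and can reasonably be expected to influence operating time, although the documents give no figure for this. If extent is not used in the analysis, the spread it causes stays in the error term of the duration comparison.

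The trial has 30 patients per arm and was not sized for duration. Depending on the spread of operating times, a real 9-minute saving could be reported as no significant difference and then read as evidence of no effect. In addition, neither named test estimates a difference in minutes, so as written the plan has no analysis that answers its own expectation about duration.

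**Working it through.** **Inputs from the documents.** 30 per arm and a 5% level (Sample Size; sidedness is not stated, two-sided taken here). Duration difference of 9 minutes (Introduction). Boezaart means 1.96 and 2.64, SD 0.685, power 90% (Sample Size).

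**Inputs assumed.** The SD of duration, and the correlation r between a pre-operative extent score and duration. Ranges are shown for both.

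**1. The plan's own figure.** For two means, n per arm = 2 × SD² × (1.960 + 1.282)² / difference² = 2 × 0.685² × 3.242² / 0.68² = 21.3, so 22 per arm (44 in total), not 30. A one-sided test gives 18 per arm. The stated 60 is therefore not reproduced, but it errs on the generous side: with 30 per arm, power for the Boezaart difference is about 97%. This does not affect the duration point; it shows only that the sample size carries no information about duration.

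**2. Power for 9 minutes without adjustment.** The standard error of the difference is SD × √(2/30). Power comes from the noncentral t distribution with 58 degrees of freedom and noncentrality 9 / (SD × √(2/30)). The 95% CI half-width is 2.002 × SD × √(2/30). The difference detectable with 80% power is 0.7356 × SD.

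| Assumed SD (min) | Power for 9 min | 95% CI half-width (min) | Detectable at 80% power (min) |
|---|---|---|---|
| 10 | 93% | 5.2 | 7.4 |
| 12 | 82% | 6.2 | 8.8 |
| 15 | 63% | 7.8 | 11.0 |
| 20 | 40% | 10.3 | 14.7 |
| 25 | 28% | 12.9 | 18.4 |
| 30 | 21% | 15.5 | 22.1 |

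Solving for the SD: power is 90% at an SD of about 10.6 minutes, 80% at about 12.2, and 50% at about 17.5.

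**3. Gain from one covariate.** Residual SD = SD × √(1 − r²). With r = 0.6 the factor is √(1 − 0.36) = 0.8, so the confidence interval narrows by 20%.

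| Assumed SD (min) | Unadjusted | r = 0.5 | r = 0.6 | r = 0.7 |
|---|---|---|---|---|
| 15 | 63% | 75% | 81% | 89% |
| 20 | 40% | 51% | 57% | 67% |
| 30 | 21% | 26% | 30% | 36% |

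The degree of freedom spent on the covariate (57 instead of 58) changes power by less than 0.1 percentage point. At SD 15 with r = 0.6 the residual SD is 12 and power is 0.815, shown as 81% after that loss.

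**The case against.** The strongest reply is that duration is a by-product. It is absent from the Objective, the Hypothesis and the sample size, and the Introduction presents it as an extra benefit. Low power for a measure that a trial was not sized for is common and is not in itself a design error. That stands, and it lowers the weight of the point. It does not remove it, because the plan states that surgery will be shorter and collects the data to show it.

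A reader might infer more than the documents support, in four ways:

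- **That a 9-minute effect would probably be missed.** This needs an SD above about 17.5 minutes. The documents give neither an SD nor a mean duration. At SD 15 a true 9-minute saving would be detected more often than not, and at SD 10 nearly always.
- **That chance imbalance in extent biases the result.** If half the patients had extensive disease (assumed), the arms would differ by 20 percentage points or more about 20% of the time (hypergeometric, 60 patients, 30 per arm: 0.196). But allocation is random, and the unadjusted test's error rate and confidence interval already allow for such imbalance. What adjustment buys is precision.
- **That the information would be lost for good.** Extent could probably be taken from pre-operative records later. What would be lost is prespecification, and with it the credibility of an adjustment chosen after the results are seen.
- **That the Boezaart comparison is equally exposed.** On the plan's inputs its power is already about 97%.

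It is also fair to say that the data collection text is a short narrative, not a case record form; it does not list even age or sex. The supportable statement is that no extent measure is specified, not that none will be recorded.

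**Conclusion.** The point holds as a conditional one about precision. The plan expects shorter surgery, admits bilateral disease of any extent, names no extent measure, and names no method suited to a continuous duration. Whether 30 per arm can show 9 minutes turns on an unstated SD: adequate at about 12 minutes or less, worse than even above about 17.5, and 63%, 40% and 21% at assumed SDs of 15, 20 and 30.

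Adjusting for extent would help in proportion to its correlation with duration, which the documents do not give. At larger SDs it would still leave the comparison underpowered. No systematic bias is shown, and no material threat to the Boezaart result. The change is worth making because it is cheap and is most credible when fixed in advance.

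**What to change.** - **Before allocation**, enter on the data sheet one extent score from the existing pre-operative work-up, such as a CT stage or the number of sinuses listed for opening. Add polyps (yes/no) and primary or revision surgery as descriptive fields.
- **In Data Analysis**, state that duration will be compared between arms by a linear model (ANCOVA) with the extent score as the single prespecified covariate.
- **In reporting**, give the difference in minutes with its 95% CI, and say in advance that a non-significant result will not be read as ruling out the cited 9 minutes.
- **Optionally**, use the same covariate in the Boezaart comparison, where the need is smaller.

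The cost is three data fields, a few minutes of entry per patient and one degree of freedom. It needs no extra patients, staff or procedures.
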